## **4 TRIAL POPULATION**

### **4.1 Screening data**

The overall recruitment period will be provided in months. The number of screened patients, number of patients included in each phase of DIVE-1 study, with the reason for non-inclusion will be reported according to flow diagram (figure 1).

### **4.2 Eligibility**

[figure not shown]
The trial inclusion and exclusion criteria are full detailed in clinical trial protocol. The number of ineligible patients screened and not included will be provided according to flow diagram (figure 1).

### **4.3 Withdrawal/Follow-up-level of withdrawal**

The level of withdrawal will be tabulate and classified as:

- Withdrawn consent from follow-up but allow data to be used until the date of consent withdrawal
- Withdrawn consent from follow-up and did not allow data to be used until the date of consent withdrawal
- Withdrawal due to lost to follow-up
- Withdrawal due to investigator decisions

The timing of withdrawal and reasons for withdrawal will be provided according to flow diagram (figure 1).

**Figure 1. Flow of participation in the DIVE-1 study.**

\* Reasons will be provided. † Level of consent withdrawal will be provided

#### 4.4 Baseline patient characteristics

Detail of baseline characteristics are reported in table 2, for each population analysis according to the study phases. Quantitative variables will be expressed as median (range values) and categorical variables will be expressed as frequencies and percentages. The number of missing data will be also reported. No formal statistical comparisons will be done.

**Table 2.1. Baseline characteristics of patients included in safety Phase I part (titration of ICV dopamine)**

Age (years)
Sex
Body mass index (kg/m  )
Disease duration since the first symptoms (years)
Disease duration since diagnosis (years)
Duration of L-dopa (years)
Duration of motor fluctuations (years)
Duration of dyskinesia (years)
Hoehn & Yahr of symptoms progression
Schwab & England activities of daily living
MDS-UPDRS total score of handicap
MDS-UPDRS motor handicap, part III (Off drug)
MDS-UPDRS motor handicap, part III (On drug)
L-Dopa sensitivity (%)
LEDD (mg)

**Table 2.2. Baseline characteristics of patients included in efficacy Phase II part (cross-over design)**

	Overall	First sequence of treatment	Second sequence of treatment
Age (years)			
Sex			
Body mass index (kg/m  )			
Disease duration since the first symptoms (years)			
Disease duration since diagnosis (years)			
Duration of L-dopa (years)			
Duration of motor fluctuations (years)			
Duration of dyskinesia (years)			
Hoehn & Yahr of symptoms progression			
Schwab & England activities of daily living			
MDS-UPDRS total score of handicap			
MDS-UPDRS motor handicap, part III (On drug)			
MOCA			
L-Dopa sensitivity (%)			
LEDD (mg)			

**Table 2.2. Baseline characteristics of patients included in long-term follow-up phase (maintenance of ICV dopamine efficacy)**

Age (years)
Sex
Body mass index (kg/m  )
Disease duration since the first symptoms (years)
Disease duration since diagnosis (years)
Duration of L-dopa (years)
Duration of motor fluctuations (years)
Duration of motor dyskinesia (years)
Hoehn & Yahr of symptoms progression
Schwab & England activities of daily living
MDS-UPDRS total score of handicap
MDS-UPDRS motor handicap, part III (On drug)
MOCA
L-Dopa sensitivity (%)
LEDD (mg)

## 5 Analysis

Data analysis will be performed by an academic statistician from Biostatistics Department of University of Lille (France) under the responsibility of [name].

### 5.1 Outcome definitions

#### 5.1.1. Phase I

**Primary outcome:** Feasibility of DIVE treatment (ICV dopamine administration) assessed in term of safety evaluated by occurrence of any adverse effects, assessed by an independent monitoring committed to decide whether to continue or stop the treatment.

The following complications will be considered for safety evaluation:

- Serious infection involving the vital prognosis of the patient
- Serious haemorrhage involving the vital and functional prognosis of the patient
- Frank worsening of the motor and/or non-motor symptoms of Parkinson's disease in a sudden or rapid manner over a month (i.e. more than double the points of classic aggravation over 3 months or more than 6 points of the total MDS UPDRS score over a month with the optimal dose of A-dopamine: best on condition)
- Neurological deficit apart from symptoms of Parkinson's disease
- Status epilepticus
- Death during the postoperative period
- Any modification of following parameters (blood pressure, pulse, ECG blood and urinary levels of dopamine and its metabolites (HVA and 5-cysteinyl-dopamine)) after stopping the titration

#### 5.1.2. Phase II

#### **Primary outcome:**

Percent Time Over target (PTO) assessed by actimetry (from first and last recording weeks of each study period) with the Parkinson KinetoGraph (PKG) system from the Global Kinetics Corporation (GK) laboratory. The PTO is the sum of the PTO for bradykinesia and for dyskinesia. The over target bradykinesia is the percentage of time the subject was bradykinetic. This is the proportion of time in bradykinesia score (BKS) severity level 3 or above (% of 2-min periods with >BKS 26) after removing artifacts. Higher values represent more epochs that the subject was severely bradykinetic. The

percentage over target dyskinesia is the percentage of time the subject was dyskinetic during the recording period between 9 am and 6 pm (% of 2-min periods with dyskinesia score (DKS) >10 above target).

***Secondary outcomes of efficacy:***

- Other validated actimetry criteria calculated every 2 minutes throughout the first and last recording weeks of each study period.
  - The PTO bradykinesia
  - The PTO dyskinesia
  - Fluctuation Dyskinesia score (estimating the amount of variability in relation to optimal control, i.e. insufficient control (bradykinesia) or overdose (dyskinesia); expected benefit with a reduction in %)
- Patient diary measures during the first and last weeks of each study period.
  - Time in good autonomy is expressed in % is the percentage of time in On state or with slight dyskinesia or slight off.
  - Time in perfect control is expressed in % or in hours (h) and represents the time in On state without dyskinesia
  - Time in “on” time without troublesome dyskinesia is expressed in % and represents the Time On with or without slight dyskinesia
  - Time in “on” time without dyskinesia and/or with slight dyskinesia and/or with slight bradykinesia is expressed in %
  - Time in dyskinesia is expressed in % and represents the time with slight, moderate or severe dyskinesia
  - Time in severe dyskinesia (%)
  - Time in severe bradykinesia = Time in severe off (%)
- Clinical criteria at end of study treatment period (V2 for first sequence treatment and V4 for second sequence treatment)
  - MDS-UPDRS part IV

- Dyskinesia rating scale (DRS) score
- The abnormal Involuntary Movement Score (AIMS)
- MDS-UPDRS parts II (on periods) III (on drug)

***Secondary outcomes of safety:***

- MDS-UPDRS parts I
- Epworth Sleepiness Scale and Parkinson's Disease Sleep Scale
- Cognitive measures (MOCA, NPI, PAS, LARS and ECMP)
- Psychiatric tolerance: a score from a simple questioning on the disorders (no thymic, anxious, psychotic decompensation).
- Frequency of adverse events during the 4 weeks of treatment period reported by the patient and/or noted by the investigator according to clinical examination, ECG, blood pressure, pulse and biological assessment (standard biology, biological iron assessment, blood and urinary levels of dopamine and its metabolites (HVA) and variations in weight, temperature, and blood pressure on the orthostatic hypotension test.

***Exploratory outcomes:***

- Actimetry criteria
  - The 50th percentile of the available bradykinesia score (BKS) (50 percentile: normal value =18.6)
  - The 50th percentile of the available dyskinesia score (DKS) (50 percentile: normal value = 4.3)
  - The percentage of time of immobility (PTI), which represents the absence of movement during recording
  - Percentage of time with a tremor (PTT)
- Clinical criteria at end of study treatment period (V2 for first sequence treatment and V4 for second sequence treatment)
  - PDQ39 score
  - Schwab and England scale score
- Biological modification between the two periods of treatment

- blood and urine determinations of dopamine, and its metabolites HVA and 5-cysteinyl-dopamine after 2 hours of treatment in the morning on an empty stomach (either 2 hours after the first oral treatment or 2 hours after the first daytime dose of A-dopamine)
- markers of oxidative stress (MDA, 4-HNE, 8 oxoDG)
- markers of axonal destruction (light chain filaments) in blood
- Pharmacogenetic parameters of dopamine metabolism (DaT, COMT, MAO, DDC, ceruloplasmin) which may influence the response to L-dopa on the reduction of dyskinesia and off period

### **5.1.3 Long term follow-up phase**

#### ***Primary outcome:***

- Percentage in “on” time without dyskinesia and with or without slight bradykinesia

#### ***Secondary outcomes of efficacy:***

- Patient diary measures
  - Time in good autonomy is expressed in % is the percentage of time in On state or with slight dyskinesia or slight off.
  - Time in perfect control is expressed in % or in hours (h) and represents the time in On state without dyskinesia
  - Time in “on” time without troublesome dyskinesia is expressed in % and represents the Time On with or without slight dyskinesia
  - Time in “on” time without dyskinesia and/or with slight dyskinesia and/or with slight bradykinesia is expressed in %
  - Time in dyskinesia is expressed in % and represents the time with slight, moderate or severe dyskinesia
  - Time in severe dyskinesia (%)
  - Time in severe bradykinesia = Time in severe off (%)
- Clinical criteria at end of study treatment period (V2 for first sequence treatment and V4 for second sequence treatment)
  - MDS-UPDRS parts II, III and IV

- The abnormal Involuntary Movement Score (AIMS) and the Dyskinesia rating scale (DRS) score

***Secondary outcomes of safety:***

- MDS-UPDRS parts I
- Epworth Sleepiness Scale and Parkinson's Disease Sleep Scale
- Cognitive measures (MOCA, NPI, PAS, LARS and ECMP)
- Psychiatric tolerance: a score from a simple questioning on the disorders (no thymic, anxious, psychotic decompensation).
- Frequency of adverse events during the 4 weeks of treatment period reported by the patient and/or noted by the investigator according to clinical examination, ECG, blood pressure, pulse and biological assessment (standard biology, biological iron assessment, blood and urinary levels of dopamine and its metabolites (HVA and 5-cysteinyl-dopamine) and variations in weight, temperature, and blood pressure on the orthostatic hypotension test.

***Exploratory outcomes:***

- Clinical criteria at end of study treatment period (V2 for first sequence treatment and V4 for second sequence treatment)
  - PDQ39 score
  - Schwab and England scale score

## 5.2 Analysis methods

### 5.2.1 Phase I

A case-report analysis will be done for phase I part of DIVE-1 study, with the following safety go no go rule: 1) In no or at most one serious and unexpected adverse events (apart from the rare surgical risks of haemorrhage and infection with no impact in vital and functional prognosis of the patient) in the first five patients, 15 other patients may be included in Phase I and the phase II will be start.

2) If two or more serious or unexpected adverse events (apart from the rare surgical risks of haemorrhage and infection with no impact in vital and functional prognosis of the patient) occur in first five patients, only 5 new patients could be included, and the following rule will be proposed to the independent Monitoring Committee to start the phase II:

- in the no or at most one serious and unexpected adverse events in the 5 new patients, 10 other patients may be included in Phase I and phase II will be start.

- if two or more serious or unexpected adverse events, the Independent Monitoring Committee could decide to stop the study without start the phase II trial.

### 5.2.2 Phase II

The phase II part of study follow a cross-over randomized design in 2 treatment sequences including **Experimental** (ICV dopamine treatment) and **Standard** (oral dopamine treatment optimized per os) treatments.

We will used to define the statistical methods the following notations:

- 3) a sequence noted E-S to define the patient's group which received ICV dopamine in first period following by oral dopamine in second period,
- 4) a sequence S-E to define the patient's group which received oral dopamine in first period following by ICV dopamine in second period.
- 5) E1 designates the value of the endpoint in the first period for the experimental treatment.
- 6) S1 designates the value of the endpoint in the first period for the standard treatment.
- 7) E2 designates the value of the endpoint in the second period for the experimental treatment.
- 8) S2 designates the value of the endpoint in the second period for the standard treatment.

***Primary outcome:***

A case-report descriptive analysis will be done by reporting individual values of primary outcome according to the two periods as well as by using spaghetti plots showing the individual change from control to experimental period (by indicating the sequence of treatment). We also reported the mean, median and range values for control and experimental period. To assess the treatment effect (experimental vs. standard treatment) on primary outcome, we will use a Wilcoxon 'signed rank test. We will also report the standardized differences (Hedges'g) calculated from the within-patient's differences (E1-S2 and E2-S1) as effect size (calculated on rank transformed data).

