In second efficacy phase II, 20 patients will be enrolled after terminating the titration phase I without complications and randomized in two groups according to cross-over design of 2 treatment periods of 4 weeks separated by a therapeutic switch carried out in the hospital. The previous treatment will be stopped at the end of period 1 and replaced by the new treatment, after 3 weeks of washout. During the 2 treatment periods and washout period, the patients will be treated by oral L-dopa at optimized dose. In summary, patients will be randomized into two groups according to the following treatment sequences:

- group 1 (n=10): period 1(ICV dopamine treatment + oral L-dopa at optimized dose) vs. period 2 (oral treatment at optimized dose + ICV Placebo treatment)
- group 2 (n=10): period 1: (oral treatment optimized + ICV Placebo treatment) vs. period 2 (ICV dopamine treatment + oral L-dopa at optimized dose)

At the end of phase II, all patients are invited to continue to use ICV dopamine treatment over the long term with the dose that allows satisfactory motor control (less than 1 hour of moderate or severe off per day and less than half an hour of dyskinesia) with or without a minimal residual dose of oral dopaminergic therapy.

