## 2.2 Randomisation

For the phase II part of the DIVE-1 study, patients are randomized in 2 treatment sequences according to a balanced plan (1:1) by using a randomization list generated by computer and provided by an independent statistician of CHU of LILLE. The randomization list will be implemented into the eCRF developed with Clinsight software. Patients will be randomized as soon as possible after having completed the phase I part of study (patients reached, at this time, a balanced titration established within 9 weeks).

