## 2.3 Sample size

Full details of the sample size are described within the clinical trial protocol and was determined according to the phase II part of study. We planned to dispose to 20 patients analysable (who completed the two-treatment sequence in phase II without major protocol deviations) to have a power >80% to detect, with a two-sided test at 0.05 significance level, an absolute decrease in PTO of 10% in intervention period compared to control period, by assuming a standard deviation of 15% and a correlation of 0.5 between the repeated measures.

The sample size was revised in 23 February 2023 following an amendment regarding the ability of central pharmacy of Lille university hospital to ensure the weekly production of experimental treatment in safe condition for a maximum of 12 patients. Regarding the proof of concept phase II study, the number of 12 patients was considered acceptable to provide first evidences of efficacy (by interpreting effect size on primary outcome and by a detailed descriptive analysis of changes in secondary outcomes in each period). During the data blind review, only 9 patients have available complete data on primary outcome and could be analysed.

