### **3 STATISTICAL PRINCIPLES**

#### **3.1 Confidence intervals and p-values**

All applicable statistical tests will be 2-sided and will be performed using a 5% significance level.

No statistical comparisons will be done for secondary objectives, only a descriptive analysis will be performed and we will report standardized differences between active and control period as effect sizes.

All confidence intervals (CIs) presented will be 95%CI and 2-sided.

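### The only phase II hypothesis test pools both treatment sequences and takes no account of period, although 9 patients cannot divide equally and the two periods start from different conditions

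*SAP*

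**What the plan says.** Section 5.2.2 defines the endpoint by treatment and period (E1, S1, E2, S2) in two randomised sequences, E-S and S-E. For the primary outcome it then says: "To assess the treatment effect (experimental vs. standard treatment) on primary outcome, we will use a Wilcoxon" signed-rank test. The effect size (Hedges' g on ranks) uses E1-S2 and E2-S1 together. Sequence appears only as a marking on the individual plots. Section 5.5 lists no sensitivity analysis.

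Four other places bear on this:
- Section 2.3, on the number available: "only 9 patients have available complete data on primary outcome and could be analysed". The split by sequence is not given. Section 3.3 limits the efficacy population to completers without major deviation.
- Section 2.2, on entry to period 1: "Patients will be randomized as soon as possible after having completed the phase I part of study". Phase I is the titration on intraventricular dopamine.
- Section 2.1, on entry to period 2: "The previous treatment will be stopped at the end of period 1 and replaced by the new treatment, after 3 weeks of washout".
- Section 5.1.2 takes the primary outcome (PTO) "from first and last recording weeks of each study period", while section 5.2.2 treats each of E1, S1, E2 and S2 as one value. No rule for combining the two weeks is given.

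**The concern.** In a two-period cross-over, the experimental-minus-standard difference carries the period effect with one sign in sequence E-S and the opposite sign in S-E. Comparing the sequences removes it. Pooling the differences in a one-sample test cancels it only on average, and only if the sequences are equal in size. Nine is odd, so they cannot be.

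As this SAP describes the trial, the periods also start differently: period 1 follows titration on active treatment with no washout described, and period 2 follows three weeks of washout. At stake are the only hypothesis test in phase II and the effect size, on which section 2.3 rests the case for the reduced sample.

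**Working it through.** **Inputs.** From section 2.3: "We planned to dispose to 20 patients analysable", power above 80%, "an absolute decrease in PTO of 10% in intervention period compared to control period", SD 15, correlation 0.5, and 9 patients now analysable. From section 3.1: "All applicable statistical tests will be 2-sided and will be performed using a 5% significance level". The period difference pi (period 2 minus period 1) is not in the SAP. It is an assumption here, shown at 5 and 10 PTO points in both directions.

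**Step 1: the plan's own figure.** SD of the within-patient difference = 15 × √(2 × (1 − 0.5)) = 15. A paired t-test with n = 20 and a 10-point difference has power 0.807, so the stated figure is reproduced. With n = 9 and no period difference, power is 0.42 (paired t) or 0.36 (exact signed-rank, true level 0.039).

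**Step 2: bias.** With treatment effect tau, E1-S2 has expectation tau − pi and E2-S1 has tau + pi. The pooled mean is tau + pi × (n_SE − n_ES)/9. In absolute value, for pi = 10:
- 5:4 split: 10 × 1/9 = 1.1 points
- 6:3 split: 10 × 3/9 = 3.3 points
- 7:2 split: 10 × 5/9 = 5.6 points

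**Step 3: spread.** The opposite shifts also widen the pooled distribution in balanced sequences. At the planned 10:10 there is no bias, yet signed-rank power falls from 0.79 to 0.75 at |pi| = 5 and 0.64 at |pi| = 10. The rank-sum test by sequence stays at about 0.76.

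**Step 4: operating characteristics with 9 patients.** Simulated normal differences, SD 15, true effect −10. The comparator is the exact rank-sum test of period 1 minus period 2 differences between sequences. Paired values are for the unfavourable and favourable sign of pi.

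| Split | pi | Signed-rank power | Rank-sum power |
|---|---|---|---|
| 5:4 | 0 | 0.36 | 0.30 |
| 5:4 | ±5 | 0.29 or 0.35 | 0.30 |
| 5:4 | ±10 | 0.17 or 0.27 | 0.30 |
| 6:3 | 0 | 0.36 | 0.34 |
| 6:3 | ±10 | 0.10 or 0.41 | 0.34 |

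The 0.41 exceeds 0.36 because there the bias favours the treatment.

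**Step 5: type I error of the signed-rank test at |pi| = 10.** About 0.017 at 5:4, about 0.035 at 6:3 and about 0.08 at 7:2.

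**Step 6: limit of the rank-sum test.** Its smallest two-sided p-value is 2/126 = 0.016 at 5:4, 2/84 = 0.024 at 6:3 and 2/36 = 0.056 at 7:2. It can never reject at 7:2. A period-adjusted t-test there has power 0.30.

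**Step 7: carry-over instead of a period effect.** Suppose residual titration dopamine lowers S1 by 5 or 10 points and nothing else differs. At 5:4 (E-S:S-E), signed-rank power is 0.23 or 0.11 and rank-sum power 0.18 or 0.09. The pooled mean is −7.8 or −5.5 and the period-adjusted mean −7.5 or −5.0. Period adjustment does not remove this problem.

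**The case against.** The strongest reply has four parts.

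- **The period difference is inferred.** A reader might conclude that the design builds one in. The SAP does not show that. It gives no size, oral L-dopa continues through both periods and the washout, and section 2.1 refers to the protocol, which is not at hand, for the detail of each phase. This stands: the difference is plausible, no more.
- **The harm is often modest.** A reader might conclude that the test's power is destroyed. At 5 points and 5:4, the planned test has 0.29 to 0.35 against 0.30 for the replacement, so nothing is gained. A large loss needs about 10 points, two thirds of an SD, and usually the unfavourable sign. Most of the shortfall from 80% comes from having 9 patients. This stands too.
- **False positives are not the general problem.** Type I error is below nominal at 5:4 and 6:3. It rises only at a split such as 7:2, which 1:1 allocation makes less likely and where the rank-sum test is unusable.
- **The most concrete mechanism is carry-over.** A placebo week directly after titration affects S1 alone, and Step 7 shows that the rank-sum test does not cure it.

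The case-report presentation, with individual values and sequence-marked plots, would make a gross period pattern visible. It does not adjust the test or the effect size. The SAP does not spell out which differences enter the signed-rank test, but its revision history calls the test paired and the effect-size sentence names the pooled differences, so pooling is the natural reading.

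**Conclusion.** The point holds in a limited form. The primary test and its effect size ignore period. With 9 patients any additive period difference biases the pooled estimate, by one ninth of its size at 5:4 and one third at 6:3, and no sensitivity analysis would quantify this. For an assumed 10-point difference, power moves from 0.36 to between 0.10 and 0.41 depending on split and sign; for 5 points at 5:4 the change is small. These figures rest on normal differences with SD 15, a true 10-point effect, an additive period effect and an unreported split.

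The SAP does not support the stronger readings that a period difference is certain, that the test generally rejects too often, or that period adjustment would settle the titration problem. The missing rule for combining the two recording weeks is a separate gap in the endpoint definition. It matters here because the first week is where carry-over into a placebo first period would be expected to show. The point should be fixed, and it does not invalidate the plan.

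**What to change.** Before unblinding, amend section 5.2.2 as follows.

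1. Report how the 9 patients divide between the sequences.
2. Pre-specify a period-adjusted analysis of the primary outcome with estimate and 95% CI. If each sequence has at least 3 patients, use the exact Wilcoxon rank-sum test of the period 1 minus period 2 differences between sequences, with half the Hodges-Lehmann shift as the estimate (the sequences differ by (tau − pi) − (−tau − pi) = 2 tau). Otherwise use a model with a period term.
3. Compute the standardised effect size on the period-adjusted contrast as well.
4. State that period adjustment does not remove carry-over of titration dopamine into a placebo first period.
5. Keep the stated endpoint, fix one rule for combining the first and last recording weeks into a single value per period, and show the last-week PTO alone as a supportive analysis addressing that carry-over.

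The cost is SAP wording and a few lines of code. If there is no period effect, the rank-sum test has power 0.30 (5:4) or 0.34 (6:3) instead of 0.36. Dropping the first recording week from the endpoint altogether is debatable and is not needed.

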***Secondary outcomes:***

For secondary and exploratory quantitative outcomes, only a descriptive analysis will be done by reporting the mean, median and range values as well as plotting the values using spaghetti plots showing the change from control to experimental period (by indicated the sequence of treatment using dedicated colors). We will also report the standardized differences (Hedges'g) calculated from the within-patient's differences (E1-S2 and E2-S1) as effect size (calculated on rank transformed data). The frequency of adverse events during the 4 weeks of treatment period will be reported in each treatment group without statistical comparison.

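### The phase II effect size is Hedges' g on rank-transformed data, but section 5.2.2 does not say what is ranked, and one natural reading gives a constant of about +1.65

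*SAP*

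**What the plan says.** - **Primary outcome (SAP 5.2.2).** Individual values, spaghetti plots, and the mean, median and range per condition are reported. A Wilcoxon signed-rank test is performed. A Hedges' g is added, "calculated from the within-patient's differences (E1-S2 and E2-S1) as effect size (calculated on rank transformed data".
- **Secondary and exploratory quantitative outcomes (SAP 5.2.2).** "For secondary and exploratory quantitative outcomes, only a descriptive analysis will be done by reporting the mean, median and range values", with plots and the same g, again "as effect size (calculated on rank transformed data". There is no test. Section 3.1 agrees: for secondary objectives, "we will report standardized differences between active and control period as effect sizes".
- **Role of the effect size (SAP 2.3).** The original plan was for 20 analysable patients. The reduction to 12 was accepted on the ground that first evidence of efficacy would come "by interpreting effect size on primary outcome and by a detailed descriptive analysis of changes in secondary outcomes in each period". At the blind review, "only 9 patients have available complete data on primary outcome and could be analysed".

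Section 5.2.2 does not state whether the differences, their absolute values with signs attached, or the original observations are ranked. It specifies no interval estimate of the within-patient difference.

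**The concern.** Hedges' g is a mean divided by a standard deviation, with a small-sample factor. Ranking changes both parts, and the change depends on what is ranked. If the differences themselves are ranked, the mean and SD of the ranks are fixed by the number of patients, so g carries no information about treatment. The sentence in section 5.2.2 invites that reading, because it names the within-patient differences and then says the calculation is on ranks.

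Two analysts following the SAP could therefore report values of opposite sign from the same nine patients. If the reading is settled only after unblinding, the choice can be influenced by the result. For secondary outcomes the exposure is greater: with no test, g is the only figure that compares the two conditions, and under the first reading every untied outcome with nine patients would show the same apparently large effect.

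**Working it through.** **Inputs (SAP 2.3 and 5.2.2).** Planned PTO decrease 10 points, SD 15, within-patient correlation 0.5, two-sided 0.05, 20 patients planned, 9 analysable. Differences are E minus S, so a negative value is a reduction in PTO, the direction planned in section 2.3.

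**The plan's own figure.** SD of the difference = 15 × √(2 × (1 − 0.5)) = 15. Paired t-test power by the noncentral t at n = 20 is 0.807, which reproduces "to have a power >80% to detect, with a two-sided test at 0.05 significance level". The assumptions are therefore read correctly. The planned standardised effect is 10/15 = 0.67 before small-sample correction.

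**Formula for g.** g = J × mean/SD, with J = 1 − 3/(4 × 8 − 1) = 0.903 for 8 degrees of freedom.

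**Reading (a): rank the nine differences.** The ranks are 1 to 9, with mean 5 and SD 2.739. So g = 0.903 × 5/2.739 = +1.649 for every untied data set. Simulated trials at true effects of 0, −5, −10, −20 and −30 points all returned this value, with no variation.

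**Reading (b): signed ranks.** The size of g cannot exceed 1.649, and it reaches that value when all nine differences share a sign. Illustrative data sets with mean differences of −0.5 and −29.7 points both gave −1.649. Under the SAP's assumptions the chance that all nine differences are negative is Φ(δ/15)⁹, where δ is the true reduction:
- 10 points: Φ(0.667)⁹ = 0.07
- 20 points: Φ(1.333)⁹ = 0.42
- 30 points: Φ(2)⁹ = 0.81

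**Reading (c): rank the 18 pooled observations, then difference.** The result depends only on ordering. Suppose control values lie 5 points apart and every patient falls by less than 5 points. Each patient's E value then ranks just below his or her own S value, all nine rank differences are −1, their SD is 0, and g is minus infinity, however small the benefit.

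**Comparison with raw g.** Median over 20,000 simulated trials of nine patients:

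| True effect (points) | Raw g | (a) | (b) | (c) |
|---|---|---|---|---|
| 0 | 0.00 | 1.65 | 0.02 | 0.01 |
| −5 | −0.31 | 1.65 | −0.30 | −0.29 |
| −10 | −0.62 | 1.65 | −0.60 | −0.59 |
| −20 | −1.25 | 1.65 | −1.37 | −1.25 |
| −30 | −1.88 | 1.65 | −1.65 | −1.94 |

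**Precision of a difference in PTO points.** The t-based 95% half-width at n = 9, if the SD of the difference is 15, is 2.306 × 15/√9 = 11.5 points.

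**The case against.** The case for leaving the text alone has several sound parts.

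- A reader might infer that the planned effect size cannot show a treatment effect at all. That holds only for reading (a). Readings (b) and (c) are near zero under no effect and about −0.6 at the planned effect, close to raw g.
- Any standardised difference is unit-free and can score a small, consistent change above a large, variable one. Raw g shares this, so the absence of PTO units is not peculiar to ranking.
- g is not the sole result for the primary outcome. Nine individual pairs, plots, summary statistics and the Wilcoxon test are planned, so direction and size can be seen patient by patient, and the mean difference follows from the two reported means.
- A reader might infer that section 5.2.2 breaches section 3.1 by giving no CI. It does not: section 3.1 sets the level and sidedness of the CIs that are presented and promises none for phase II.
- A reader might also ask for a power figure for nine patients. The SAP ties its power statement to 20 patients, reports the reduction openly and claims no power for nine, so there is no error to correct.

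All of this stands, and it limits the point. It does not remove it: the calculation remains unfixed, one natural reading is uninformative, and the individual values and the test do not supply an estimate of the paired difference with its uncertainty.

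**Conclusion.** The concern holds as an ambiguity with a concrete consequence. On identical data the phase II g can be +1.65 or −1.65 depending on an unstated choice. One natural reading gives +1.65 for any untied data at n = 9; another is capped at 1.65 in size, with the cap reached in about 7%, 42% and 81% of trials at true reductions of 10, 20 and 30 points; the third reflects only the ordering of the values. The percentages and medians assume normal data with the SD and correlation in section 2.3. The constant in reading (a) and the cap in reading (b) need only nine untied differences, none of them zero.

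The point has weight because section 2.3 leans on the effect size to accept the smaller sample, and because section 5.2.2 gives secondary outcomes no other comparative statistic. It does not show that the primary analysis as a whole is uninformative.

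**What to change.** In SAP 5.2.2, under both the primary and the secondary outcomes:

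1. Delete the bracketed phrase on rank transformation. State that Hedges' g is computed on the untransformed within-patient differences (E1−S2 and E2−S1), and report it with a 95% CI.
2. For the primary outcome, add the Hodges-Lehmann estimate of the within-patient difference in PTO points with its exact 95% CI. This is the estimate that matches the planned Wilcoxon signed-rank test. Because the signed-rank distribution is discrete, the attained level at n = 9 is 1 − 2 × 10/512 = 96.1%, since 10 of the 512 sign patterns give a rank sum of 5 or less. A footnote should say so.

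Section 3.1 does not contain the phrase and needs no deletion.

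The cost is a few lines of text and code, with no new data. The interval will be wide: its half-width of about 11.5 points (t-based, under the SAP's assumptions) exceeds the planned 10-point effect, and the report will have to show that. The wording should be settled before the treatment codes are used in the analysis.
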